Neuromodulation in Lower Limb Amputees

NCT 04543786

Last document update: Mar. 17, 2022

Background:

Limb amputation results in an extreme form of peripheral nerve injury. Damage to peripheral nerves, such as with neuropathy, crush injuries, nerve transection, or limb amputation often results in chronic pain, which may be associated with altered excitability of spinal sensorimotor pathways. These spinal pathways become hyperexcitable due to a lack of sensory input, which causes tonic disinhibition of descending circuits and spontaneous activity in the dorsal root ganglia. Spinal excitability can be measured using the H-reflex, in which electrical stimulation of muscle spindle Ia afferents activates spinal motoneurons via the myotatic reflex, as well as the posterior root-muscle (PRM) reflex, which is elicited by transcutaneous stimulation over the dorsal roots and is considered to be half of the H-reflex, excluding the peripheral primary afferents, but with multiple root activation. Spinal excitability has not been measured in amputees but may offer a potential biomarker for phantom limb pain (PLP). Neuromodulation may restore normal spinal excitability and reduce PLP, thus offering the potential to improve the quality of life in individuals with a lower limb amputation. The results of this study will provide the foundation for future development of a neuroprosthesis to restore spinal excitability and reduce PLP in individuals with a lower limb amputation.

Objectives:

The overall goal of this work is to investigate the changes in the spinal cord resulting from limb amputation. Specifically, we measured spinal cord excitability using posterior root-muscle (PRM) reflexes in people with a transtibial amputation. We hypothesized that spinal reflexes would be hyperexcitable, indicated by lower thresholds to evoke the reflexes, because of the neuropathic pain state. We applied tSCS each day for 5 days, targeting the dorsal roots corresponding to the distal limbs. We hypothesized that, after 5 days of tSCS, spinal reflex hyperexcitability and PLP would decrease.

Design:

Participants underwent 5 testing and stimulation sessions in 1 week.

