We performed the pain pressure threshold test using an algometer. The pain pressure threshold test measures the minimum amount of pressure that the participant can tolerate at a specific location. We pushed the rubber tip (1 cm diameter) of the algometer onto the skin over muscle (not pushing on bone) on several locations of both the residual and intact limbs. The participant reported when the pressure became painful, at which point we removed the algometer and recorded the pressure magnitude.

We asked participants to rate their PLP in the last 24 hours using a visual analog scale (VAS) from 0 and 10, where 0 indicated no pain at all, and 10 indicated the worst pain imaginable. Participants completed the short-form McGill Pain Questionnaire to describe their pain prior to participation in the study as well as throughout the week. The McGill Pain Questionnaire evaluates the sensation, temporal changes, and strength of pain. The total McGill Pain Questionnaire score indicates the intensity and affect the pain has on their life, and a 5-point change in McGill Pain Questionnaire is considered clinically meaningful.

We delivered bilateral tSCS for neuromodulation continuously for 30 minutes, with a break at 15 minutes to inspect the stimulation site. The tSCS consisted of 1 ms long pulses with a 10 kHz carrier frequency, delivered at 30 Hz. We started with a low amplitude of stimulation (approximately 10-20 mA) and slowly increased the stimulation beyond PRM reflex threshold, according to the comfort of the participant.

All data were collected while the participant sat comfortably in a chair. At the beginning of each day, the participant rated their PLP over the last 24 hours using the VAS. We marked the location of the stimulation and EMG electrodes with a permanent marker to ensure consistent placement across the 5 days. Every day, we performed the M-wave and PRM reflex measures, followed by high-frequency tSCS for 30 minutes. At the beginning of the first and fifth days, the participant completed the McGill Pain Questionnaire, and we performed the pain pressure threshold test.

Study Protocol for study using transcutaneous spinal cord stimulation in lower limb amputees

Before participant comes in:

1. A00 = control port on stimulator
2. P00 = trigger port on stimulator
3. A01 = DIGI port on TMSi
4. TMSi cables: HDEMG, 2x BPEMG, IMU
5. PW on stimulator = 1000 us; 100%, 10 us; Monophasic, negative; 10 V = 180 mA

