6. Close reflex GUI

Notes:

Statistical Analysis Plan

We tested for normality using the Shapiro–Wilk test and assessed the homogeneity of variance using Levene's test. A p-value < 0.05 was considered significant.

Grouped threshold data contain the mean threshold across all channels of the HD-EMG grid. We performed a linear correlation between the PRM reflex threshold for each electrode on the HD-EMG grid with its impedance value. We expressed reflex thresholds in units of charge (μC), obtained by multiplying the stimulation amplitude (in mA) by the pulse width (1 ms). To compare the PRM reflex thresholds over 5 days, we performed a one-way analysis of variance (ANOVA) with Bonferroni post-hoc tests.

We created recruitment curves for the PRM reflexes, M-waves, and F-waves by plotting the mean peak-to-peak amplitude of the response from each electrode on the HD-EMG grid as a function of stimulation amplitude. The slope of the recruitment curve corresponded to the slope of the line between the inflection points across the steepest part of the curve.

We determined the change in PPT over time by subtracting the PPT at each location on Day 1 from Day 5. We normalized the PPT at each location to the maximum PPT value recorded for each participant. We expressed the change in PPT on a scale between -1 and 1, where -1 indicated a maximal decrease in PPT, 1 indicated a maximal increase in PPT, and 0 indicated no change in PPT. We also compared the average PPT across all tested locations on each limb between day 1 and day 5 using a paired t-test.

We used repeated measures ANOVA to compare the mean VAS score from all participants across the 5 days. A decrease in the VAS score by 50% and at least 1 point is considered clinically meaningful. We summated the responses from each subsection of the MPQ to obtain a total score. A clinically meaningful decrease in MPQ score is a 5-point decrease.

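### PRM thresholds from the same participants on five days are compared by a one-way ANOVA with no participant term

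*Combined protocol and SAP*

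**What the plan says.** The Design section has every participant attend all five days: "Participants underwent 5 testing and stimulation sessions in 1 week". It adds: "Every day, we performed the M-wave and PRM reflex measures, followed by high-frequency tSCS for 30 minutes". The Objectives state the hypothesis that these data serve: "We hypothesized that, after 5 days of tSCS, spinal reflex hyperexcitability and PLP would decrease".

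The Statistical Analysis Plan then names three comparisons over time:

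- PRM threshold: "To compare the PRM reflex thresholds over 5 days, we performed a one-way analysis of variance (ANOVA) with Bonferroni post-hoc tests".
- Phantom limb pain VAS: "We used repeated measures ANOVA to compare the mean VAS score from all participants across the 5 days".
- Pressure pain threshold, averaged within each limb: compared "between day 1 and day 5 using a paired t-test".

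On the unit of the threshold data it says: "Grouped threshold data contain the mean threshold across all channels of the HD-EMG grid". The next sentence, on the correlation with impedance, uses the "PRM reflex threshold for each electrode on the HD-EMG grid". The only assumption checks named are Shapiro–Wilk and Levene. Sphericity is not mentioned.

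**The concern.** Five daily thresholds from one person are correlated. An ordinary one-way ANOVA treats the five days as five independent groups and counts the differences between people as noise. The plan uses within-person wording for VAS over the same five days and for pressure pain threshold. Its absence for PRM threshold therefore reads most naturally as an ordinary one-way ANOVA.

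Recruitment-curve slopes are defined, but no test is attached to them. The threshold ANOVA therefore carries the reflex half of the hypothesis alone. If its error term is too large, thresholds could change within people and the study could still report no change.

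**Working it through.** The documents state no power or sample size, so there is no figure of the plan's own to reproduce. Taken from the documents: 5 days, the same participants throughout, significance level 0.05. Assumed, because the documents do not give them: number of participants n, intraclass correlation (ICC), size of shift, number of channels, equal correlation between all pairs of days, and complete data.

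**Step 1. Error terms, one grid mean per participant-day.** Write threshold = mean + day effect + participant effect (variance σ_b²) + residual (variance σ_w²), with ICC = σ_b²/(σ_b² + σ_w²). The participant effect is the same on every day and cancels from differences between day means. With no true change:

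- expected mean square for day = σ_w²
- repeated-measures error, 4(n − 1) df: expectation σ_w²
- one-way error, 5(n − 1) df: expectation σ_b² + σ_w²

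The ratio of expected mean squares in the one-way test is thus 1 − ICC instead of 1. At ICC 0.5 it is half what it should be.

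**Step 2. Type I error.** Simulated at n = 10, the nominal 5% one-way test rejects in about 2.2%, 0.4% and 0.05% of trials at ICC 0.2, 0.5 and 0.7. The test is conservative.

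**Step 3. Power.** Assume a linear shift of 1.5σ_w, so the day means are 0, 0.375, 0.75, 1.125 and 1.5. The sum of squared deviations is 2 × (0.75² + 0.375²) = 1.40625, and the noncentrality of the repeated-measures F is n × 1.40625.

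- n = 5: noncentrality 7.03, df 4 and 16, critical F 3.007, power 42%
- n = 10: noncentrality 14.06, df 4 and 36, critical F 2.634, power 81%
- n = 20: noncentrality 28.13, df 4 and 76, critical F 2.492, power 99%

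The one-way and sphericity-corrected figures come from simulation, with at least 40,000 replicates per cell:

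| n | One-way, ICC 0.2 | One-way, ICC 0.5 | One-way, ICC 0.7 | RM, uncorrected | RM, Huynh–Feldt | RM, Greenhouse–Geisser |
|---|---|---|---|---|---|---|
| 5 | 31% | 13% | 5% | 42% | 38% | 21% |
| 10 | 71% | 38% | 12% | 81% | 80% | 73% |
| 20 | 98% | 86% | 47% | 99% | 99% | 99% |

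**Step 4. Where there is no loss.** At ICC 0.02 the one-way and uncorrected repeated-measures tests are level (about 81% each at n = 10; 43% against 42% at n = 5). At n = 5 the one-way test matches Huynh–Feldt at ICC 0.1 (38%) and still exceeds Greenhouse–Geisser at ICC 0.3 (25% against 21%).

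**Step 5. If channels were the replicates.** The ANOVA sentence does not exclude this. Take one participant, C channels, no true change, and a share s of the variance common to all channels on a day. The F statistic is then inflated by 1 + C·s/(1 − s). For C = 32 and s = 0.05 the factor is 1 + 32 × 0.05/0.95 = 2.684. The critical F (4 and 155 df) is 2.430, and P(F > 2.430/2.684) = 46%. False-positive rates:

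| Shared share | 16 channels | 32 channels | 64 channels |
|---|---|---|---|
| 0% | 5% | 5% | 5% |
| 2% | 12% | 21% | 39% |
| 5% | 26% | 46% | 70% |
| 10% | 47% | 71% | 88% |

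If stable offsets between channels make up 60% of the variance, the rates are lower: 11%, 33% and 64% at a 5% share.

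**The case against.** The strongest reply is that one-way counts factors, and a one-factor repeated-measures ANOVA is also one-way. The section is a short past-tense account, so the right test may have been run and under-described. The VAS wording favours the ordinary reading but does not prove it, and pressure pain threshold is a weaker comparator because it has only two time points. This stands as a limit on certainty. It does not rescue the text: as written, no participant term is there, and the two models can give opposite conclusions on the same data.

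Second, on the likelier unit (grid means) the error is conservative and its cost depends on assumed values. That is right, and Step 4 shows where the cost vanishes or reverses. A fair comparison should also use the corrected repeated-measures figures. At n = 10 those are 73% to 80%, still well above 38% at ICC 0.5.

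Third, no sentence says that channels enter the ANOVA; per-electrode thresholds appear only in the impedance correlation. Step 5 therefore supports a request to state the unit and nothing more.

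Fourth, the power figures assume complete data, and the post-hoc tests were not simulated. With stimulation limited by tolerance or 180 mA, a threshold could be missing on some days, and a classical repeated-measures ANOVA would drop that participant. This bears on the choice of remedy but does not justify omitting the participant term.

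**Conclusion.** The concern holds. Taken as written, the plan uses the wrong error term for its only named test of reflex change over time. Confidence is high on that mismatch between design and analysis; the size of the effect is conditional on the assumed values.

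With one grid mean per participant-day, a significant overall F can be believed. The damage is to a null result: at n = 10 and a 1.5 SD shift, power falls from 81% (73% to 80% corrected) to 38% at ICC 0.5 and 12% at ICC 0.7. The loss is negligible at very low ICC, and small at n = 20 with ICC 0.2. If channels were used as replicates, the direction reverses and a significant result could not be trusted.

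**What to change.** Analyse one grid-mean threshold per participant per day, with the participant as the unit. Use either a repeated-measures ANOVA with its sphericity correction named in the SAP, or a linear mixed model with day fixed and participant random. The mixed model also keeps participants with a missing day. Make the Bonferroni contrasts paired and list the day pairs; all pairs of five days give 10 contrasts, each tested at 0.05/10 = 0.005. Do not treat HD-EMG channels as independent replicates. If a one-factor repeated-measures ANOVA was run, say so.

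As a clarification, state which daily run is used. The data sheet records a threshold before (R1) and after (R2) each stimulation session. The Design text points to R1, but the SAP does not say. Either series, Day 1 to Day 5, spans four sessions of stimulation; only Day 1 R1 to Day 5 R2 spans all five.

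The cost is a change of SAP wording and one re-analysis, with no new data collection. The data sheet holds one mA value per run, so grid means come from the stored HD-EMG recordings, and those for R2 may still have to be derived if that run is chosen.

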2. **Enable** stimulator
3. Change name of file to "SubjectID_DayX_PeriphRC_R1", reset counter to 1
4. Set limits to below H-reflex threshold and above M-max
 - a. Amplitude range:
Day 1: _____ mA to _____ mA, notes: _____
Day 2: _____ mA to _____ mA, notes: _____
Day 3: _____ mA to _____ mA, notes: _____
Day 4: _____ mA to _____ mA, notes: _____
Day 5: _____ mA to _____ mA, notes: _____

5. Stimulate RC (default settings: 10 s between points, 4 reps each, 15 sweeps)

*Note: this takes 10 minutes to complete – warn the participant

6. 1.3x threshold:

Day 1 = _____mA, Day 2 = _____mA, Day 3 = _____mA, Day 4 = _____mA, Day 5 = _____mA

Peripheral rate-dependent depression:

1. Change name of file to “SubjectID_periphRDD_DayX_R1”, reset counter to 1

2. Set min and max amplitudes to 1.3x threshold

3. Stimulate 20 pulses with the time between pulses equal to 10 s (0.1 Hz)

Day 1 notes: _____

Day 2 notes: _____

Day 3 notes: _____

Day 4 notes: _____

Day 5 notes: _____

4. Stimulate 20 pulses with the time between pulses equal to 1 s (1 Hz)

Day 1 notes: _____

Day 2 notes: _____

Day 3 notes: _____

Day 4 notes: _____

Day 5 notes: _____

5. **Disable** stimulator

6. Close reflex GUI

tSCS neuromodulation:

1. Ask participant if they need a break or to use the washroom

2. Set stimulator pulse width to 40 us; output to biphasic

3. Change control of output to the dial

4. Connect bilateral stimulation lead wires

5. Open neuromod GUI (*tSCSguiControlStimv6.m*)

6. **Enable** stimulator

7. Set duration to 15 minutes (900 s), start stimulation, with low amplitude set on the dial

8. Slowly increase stimulation as they get used to the feeling and contractions

9. Set amplitude to

Day 1: _____ mA (engagement of back muscles)

Day 2: _____ mA (engagement of back muscles)

Day 3: _____ mA (engagement of back muscles)

Day 4: _____ mA (engagement of back muscles)

Day 5: _____ mA (engagement of back muscles)

10. Check skin under stimulation electrodes

11. Begin second stimulation (15 minutes (900 s))

Day 1: _____ mA (engagement of back muscles)
Day 2: _____ mA (engagement of back muscles)
Day 3: _____ mA (engagement of back muscles)
Day 4: _____ mA (engagement of back muscles)
Day 5: _____ mA (engagement of back muscles)

12. **Disable** stimulator

13. Disconnect bilateral tSCS lead

REPEAT REFLEXES – Make new folder

Record Impedances:

1. Run reflex GUI (*StimHreflexTMSiv15.m*)
2. Change name of file to “SubjectID_DayX_Impedacnes_R2”, reset counter to 1

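### PRM thresholds have one before/after hypothesis but no planned contrast for it, only Bonferroni post-hoc tests over five days with an undefined family; if that family is all ten pairs, Day 1 versus Day 5 is tested at 0.005

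*Combined protocol and SAP*

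**What the plan says.** The hypothesis about change is in the Objectives: "We hypothesized that, after 5 days of tSCS, spinal reflex hyperexcitability and PLP would decrease". It compares the state after the course of stimulation with the state before it. No intermediate day is singled out.

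The analysis of that measure is one sentence in the Statistical Analysis Plan, which says of the PRM thresholds across the five days: "we performed a one-way analysis of variance (ANOVA) with Bonferroni post-hoc tests". The significance rule is "A p-value < 0.05 was considered significant", with no statement of sidedness. The SAP does not list the day pairs to be compared, give their number, or name a planned contrast for thresholds. For pressure pain thresholds, by contrast, the same SAP uses a single paired t-test of Day 1 against Day 5.

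Two passages bear on what before and after mean. The Design narrative says "Every day, we performed the M-wave and PRM reflex measures, followed by high-frequency tSCS for 30 minutes", so the daily threshold precedes that day's stimulation. The session checklist then has a second set of reflex measurements after stimulation, under "REPEAT REFLEXES – Make new folder" (files marked R2, against R1 for the first set). The SAP does not say which set enters the ANOVA.

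**The concern.** The overall ANOVA has no direction and responds to any difference among the days. It cannot by itself show that thresholds rose between the start and the end of the course. That question falls to the post-hoc step, where the comparison of interest shares the 5% error allowance with the rest of the family. If the family is every pair of days, nine of the ten comparisons are not hypotheses of the study, and together they take nine tenths of the allowance.

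What is at stake is a missed effect. A real rise in PRM threshold by Day 5, which is the mechanistic claim, could fail the post-hoc test and be read as evidence against the mechanism when the test had little power. Because the family is undefined, it could also be fixed as four, ten or some other number after the results are seen.

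**Working it through.** **Plan's own figure.** There is none to reproduce. The documents give no sample size, power, SD or effect size.

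**Inputs from the documents.** Five days (Design: "Participants underwent 5 testing and stimulation sessions in 1 week"). Significance level 0.05 (SAP). One threshold per participant and day, since "Grouped threshold data contain the mean threshold across all channels of the HD-EMG grid".

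**Assumptions.** Two-sided tests. Standardised mean change *d* = mean change / SD of the within-person change, mainly 1.0. Number of participants *n* from 5 to 15.

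**Step 1: level per comparison.**
- All pairs: C(5,2) = 5 × 4 / 2 = 10, so 0.05/10 = 0.005.
- Each later day against Day 1: 4 comparisons, so 0.05/4 = 0.0125.
- One planned contrast: 0.05.

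**Step 2: power of Day 1 versus Day 5, paired t.** Power = P(|T| > t at 1 − α/2), where T is noncentral t with n − 1 df and noncentrality d√n. For n = 8 and d = 1.0 the noncentrality is √8 = 2.83, and the critical values on 7 df are 2.365 (α = 0.05), 3.335 (0.0125) and 4.029 (0.005).

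| n | d | α = 0.05 | α = 0.0125 | α = 0.005 | Share lost, 0.005 vs 0.05 |
|---|---|---|---|---|---|
| 5 | 1.0 | 40% | 15% | 7% | 82% |
| 8 | 1.0 | 68% | 39% | 24% | 65% |
| 10 | 1.0 | 80% | 55% | 38% | 53% |
| 15 | 1.0 | 95% | 83% | 70% | 26% |
| 10 | 0.8 | 62% | 35% | 21% | 66% |
| 8 | 1.5 | 95% | 78% | 60% | 37% |

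At d = 1.0, 80% power needs n = 10 for one contrast, 15 for four comparisons and 18 for ten.

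**Step 3: pooled error.** Post-hoc tests after an ANOVA often use the pooled residual. With a repeated-measures error on 4(n − 1) df and d = 1.0, power at 0.05 versus 0.005 is 56% versus 20% for n = 5, 78% versus 43% for n = 8 (45% lost), and 87% versus 57% for n = 10 (34% lost).

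**Step 4: what counts as after.** The Day 5 R1 threshold is taken before the Day 5 stimulation, so it follows 5 − 1 = 4 sessions. Only Day 5 R2 follows all five. The hypothesis does not say which is meant.

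**The case against.** The strongest reply is that the plan nowhere says ten pairs. A reader might infer that every pair of days is tested and that power is therefore at least halved. The documents support neither as a plain statement. The family is simply not given, and ten is the usual reading of unqualified Bonferroni post-hoc tests. With four comparisons against Day 1, the loss at d = 1.0 is already below half at n = 8 (68% to 39%). With pooled repeated-measures error and ten pairs it is also below half at n = 8. All of this stands, and it limits the size of the point. The omission of the family itself remains.

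Second, the ANOVA over days is tested at 0.05 in its own right. Assume a linear change reaching 1.0 SD by Day 5, with equal variances and correlations across days. The residual variance is then 0.5, the noncentrality is n × 0.625/0.5, and the repeated-measures F on 4 and 4(n − 1) df has power of 63% at n = 8 and 76% at n = 10. So it would be wrong to infer that Bonferroni alone decides whether anything is declared: a day effect could still be found. But that result would not say that Day 5 differs from Day 1, or in which direction.

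Third, Bonferroni does not inflate the type I error, and comparing thresholds across five days is a stated aim of the SAP, so the intermediate days are not irrelevant. Both stand. They make this a matter of efficiency and clarity, not validity.

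**Conclusion.** The point holds in conditional form. The only hypothesis about change in PRM thresholds has no planned contrast, and the family for the post-hoc tests is undefined. If the family is all ten pairs, the comparison of interest is made at 0.005. With a paired test, about 10 or fewer participants and a change of 1.0 SD or less, more than half the power is then lost. These sample sizes and effects are assumptions. The loss is under half with larger effects at moderate n, at n = 15 with a 1.0 SD change, or under the pooled-error and four-comparison readings at n = 8.

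The documents do not support reading this as an invalid analysis, nor as a fixed halving of power. Whether the one-way ANOVA treats repeated days as independent is a separate question and is not counted in these figures. The change is worth making, but the analysis is not unsafe without it.

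**What to change.** Replace the post-hoc clause with one planned contrast for the PRM threshold:

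- Compare Day 1 before tSCS (R1) with a named Day 5 measurement. State R1 or R2, and note that Day 5 R1 follows only four sessions, while Day 5 R2 follows five but is taken in the same visit as the last one.
- Estimate it within participants, from a model with participant as a random or blocking factor.
- Test it at two-sided 0.05 and report the estimate with its 95% CI.
- Report the other day pairs descriptively, or as secondary comparisons with Holm adjustment over a listed family.

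The SAP is written in the past tense. If data have already been analysed, label the contrast as not prespecified but derived from the hypothesis in the Objectives, and report the Bonferroni result beside it.

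The cost is a sentence or two in the SAP and no new data. The small downside is that differences involving intermediate days carry no confirmatory claim.

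### The planned VAS test cannot show that phantom limb pain fell: it is an omnibus repeated measures ANOVA with no directional contrast and no sphericity correction

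*Combined protocol and SAP*

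**What the plan says.** The Objectives give a hypothesis with a direction: "We hypothesized that, after 5 days of tSCS, spinal reflex hyperexcitability and PLP would decrease". For the daily pain rating, the Statistical Analysis Plan offers one inferential analysis: "We used repeated measures ANOVA to compare the mean VAS score from all participants across the 5 days". The significance rule is general and gives no sidedness: "A p-value < 0.05 was considered significant".

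The assumption checks are a Shapiro-Wilk test for normality and a check of equal variances ("assessed the homogeneity of variance using Levene's test"). Follow-up comparisons are named for the PRM reflex thresholds ("we performed a one-way analysis of variance (ANOVA) with Bonferroni post-hoc tests"), and pressure pain thresholds (PPT) get a paired t-test of Day 1 against Day 5. VAS gets neither. The next statement on VAS sets a criterion for clinical relevance, with no test attached: "A decrease in the VAS score by 50% and at least 1 point is considered clinically meaningful".

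The Design section fixes the timing: "At the beginning of each day, the participant rated their PLP over the last 24 hours using the VAS". Stimulation follows later the same day.

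**The concern.** The hypothesis asks whether pain is lower at the end than at the start. The F test asks whether the five daily means differ in any way at all. A rise, a temporary dip or an alternating pattern can each give p < 0.05, so the p-value cannot carry the conclusion the Objectives aim at. This matters because VAS is the only measure of PLP with a planned test. The McGill questionnaire has a threshold for a meaningful change but no test.

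The second issue is the error rate. The univariate repeated measures F has its nominal size only under sphericity, meaning equal variances of all between-day differences. Neither Shapiro-Wilk nor Levene checks this. Ratings of the previous 24 hours on successive days may well be more alike when the days are closer together, and that breaks sphericity.

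**Working it through.** **Inputs from the documents.** Five VAS ratings per participant, one group, threshold 0.05. No sample size, SD, effect size or within-person correlation is stated, so there is no planned figure to reproduce.

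**Assumptions.** n = 5, 8, 10, 15 and 20. Five covariance structures: compound symmetry, AR(1) with correlation 0.5, 0.7 or 0.9, and random intercept plus slope (variances 0.5 and 0.05, residual 0.3). 20,000 simulated trials per cell.

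**Tests.** The omnibus F has 5 − 1 = 4 and 4(n − 1) degrees of freedom. The Greenhouse-Geisser (GG) version multiplies both by the estimated ε. With D the double-centred covariance matrix, ε = tr(D)² / [4 tr(D²)], and ε = 1 means sphericity. The Day 5 minus Day 1 contrast is a paired t with n − 1 degrees of freedom.

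**Step 1: type I error, range over n = 5 to 20.**

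| Covariance | ε | Uncorrected F | GG F | Day 5 − Day 1 t |
|---|---|---|---|---|
| Compound symmetry 0.6 | 1.00 | 0.049–0.052 | 0.014–0.038 | 0.048–0.054 |
| AR(1) 0.5 | 0.81 | 0.061–0.062 | 0.021–0.042 | 0.049–0.052 |
| AR(1) 0.7 | 0.69 | 0.069–0.077 | 0.025–0.046 | 0.048–0.054 |
| AR(1) 0.9 | 0.58 | 0.081–0.085 | 0.031–0.049 | 0.046–0.052 |
| Random intercept and slope | 0.79 | 0.061–0.063 | 0.023–0.042 | 0.048–0.053 |

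The first row is the sanity check: under sphericity the nominal 5% is recovered. Under AR(1) the uncorrected F runs at about 6% to 8.5%, almost regardless of n. GG is conservative at small n. The contrast holds about 5% throughout.

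**Step 2: direction (n = 10, AR(1) 0.7).** The uncorrected F rejects in 50% of trials for a linear fall of 0.8 SD and in 50% for a rise of the same size. For daily means of 0, 0.8, 0, 0.8, 0 SD, where Day 5 equals Day 1, it rejects in 92%. The Day 5 minus Day 1 contrast has mean zero there, so it rejects at its nominal 5%.

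**Step 3: power (n = 10, change of 0.8 SD, two-sided 0.05).**

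| Covariance and pattern | Uncorrected F | Linear trend | Day 5 − Day 1 |
|---|---|---|---|
| Compound symmetry 0.5, linear fall | 54% | 71% | 62% |
| Compound symmetry 0.5, early drop then held | 67% | 53% | 62% |
| AR(1) 0.7, linear fall | 50% | 43% | 45% |
| AR(1) 0.7, early drop then held | 65% | 30% | 45% |

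Under AR(1) 0.7 the F column includes the benefit of an inflated size. The GG-corrected F has 39% for the linear fall and 50% for the early drop. Under compound symmetry 0.5 the GG-corrected F has 57% for the early drop.

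The contrast figures can be checked by hand. The variance of Day 5 − Day 1 is 2(1 − ρ), where ρ is the correlation between those two days. Under compound symmetry 0.5 this is 2(1 − 0.5) = 1, so the noncentrality is 0.8 × √10 / 1 = 2.53 on 9 degrees of freedom. Under AR(1) 0.7 it is 2(1 − 0.7⁴) = 1.52, so the noncentrality is 0.8 × √10 / √1.52 = 2.05. The value depends only on the two end days, which is why it is the same for both patterns.

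**Step 4: sessions covered.** Each rating precedes that day's stimulation. Day 1 follows 0 sessions and Day 5 follows 4. No VAS rating comes after the fifth session.

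**The case against.** Several counter-arguments have force. The daily means will presumably be reported, and the criterion for clinical relevance is itself a decrease, so a rise is unlikely to be presented as benefit. That lowers the risk of misreading, but it attaches no test or interval to the decrease. The inflation is moderate and conditional: the documents contain no VAS covariance data, and silence on a correction does not prove that the software applied none. Both points stand, so the claim is only that the plan specifies no protection.

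A reader might also infer that the omnibus F generally loses power. The figures do not support that. It has less power than a trend test or the end-point contrast for a linear fall under compound symmetry, where its size is correct. Under AR(1), where its size is inflated, its raw power is higher than either. For an early drop that is then held, it also has more power under compound symmetry.

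Nor does it follow that a linear trend should be the sole test. The Objectives predict a decrease, not a straight line, and for the early drop the trend does worse than even the GG-corrected F (53% against 57%, and 30% against 50%).

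Finally, the plan is written in the past tense, so a contrast introduced now may not be prospective.

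**Conclusion.** The concern holds in two parts. First, a significant result on the planned VAS test would not show that PLP decreased. This follows from the form of the test and needs no assumption about sample size or correlation; the 50%, 50% and 92% figures only illustrate it. Second, the 5% level is not protected if sphericity fails. The true level would be about 6% to 8.5% for AR(1) correlations of 0.5 to 0.9 and n = 5 to 20, all of which are assumed. With a sphericity-compatible structure there is no inflation. A general power loss is not part of the conclusion.

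**What to change.** In the Statistical Analysis Plan, make the test of the PLP hypothesis a two-sided 0.05 paired t-test of Day 5 minus Day 1 VAS, in line with the PPT analysis. Report the mean difference with its 95% CI next to the SAP's own criterion for a meaningful decrease. State that VAS is rated before each day's session, so the contrast reflects four completed sessions and not five. Keep the omnibus F as supportive, with Greenhouse-Geisser correction; a linear trend over Days 1 to 5 may be added as a further description. If the data have already been analysed, label the contrast as added afterwards.

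The change takes a few sentences and no new data. The cost is that a two-endpoint contrast ignores Days 2 to 4 and will have less power than the trend or the omnibus F for some patterns, as Step 3 shows. The supportive F keeps some sensitivity to those patterns.
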